8.2 Statistical analysis of the secondary endpoints

A patient reported HBI, completed by each patient, is included as part of the patient disease assessment. Total HBI score will be summarized by enrollment cohort and actual treatment at Baseline for each time point the assessment was collected. Change from baseline for each post-baseline assessment will also be summarized by enrollment cohort and actual treatment at Baseline.

Summary statistics will be provided for the physician assessment of disease severity by enrollment cohort and actual treatment at Baseline for each time point the assessment was collected as well as for the change from baseline for each post-baseline assessment and actual treatment at Baseline.

Summary statistics will be provided for the patient assessment of disease severity by enrollment cohort and actual treatment at Baseline for each time point the assessment was collected as well as for the change from baseline for each post-baseline assessment. The number and percentage of patients in each patient reported disease severity category (remission, mild-moderate, moderate-severe, severe) will also be presented by enrollment cohort and actual treatment at Baseline for each time point.

The physician reported total HBI score will be summarized by enrollment cohort and actual treatment at Baseline for each time point the assessment was collected. Change from baseline for each post-baseline assessment will also be summarized by enrollment cohort and actual treatment at Baseline.

The number and percentage of patients in HBI remission and HBI response, based on the physician reported HBI total score will be presented at each visit for remission and at each post baseline visit for response. The number of patients at each visit will be used as the denominator for percentage of HBI remission. The number of patients with baseline at each post baseline visit will be used as the denominator for percentage of HBI response. Analyses using actual treatment at Baseline will remove the subject from the summaries after they have switched treatment.

A listing will be provided with the physician reported individual HBI items, HBI remission, and HBI response as well as the total score and assessment of disease severity.

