3.2.2 Physician reported Harvey-Bradshaw Index

The physician reported Harvey-Bradshaw Index (HBI) is composed of 5 parameters:

1. General well-being (0=Very well, 1=Slightly below Par, 2=Poor, 3=Very poor, 4=Terrible)
2. Abdominal pain (0=None, 1=Mild, 2=Moderate, 3=Severe)
3. Number of liquid stools per day
4. Abdominal mass (0=None, 1=Dubious, 2=Definite, 3=Definite and tender)
5. Complications (1 per item: Arthralgia, Uveitis, Erythema nodosum, Aphthous ulcers, Pyoderma gangrenosum, Anal fissure, New fistula, and Abscess)

Note for #3 that if a patient is using a colostomy bag, the number of times per day the bag is emptied is counted instead.

The use of eCRFs in this registry will allow the total score to be computed and, therefore, not require the investigators to record the total HBI score. If any of the first 4 parameters are missing, then the total HBI score will be set to missing. Otherwise, the total will be the sum of available data.

In cases where HBI is collected multiple times in the same visit a worst case approach will be taken.

HBI response, determined based on physician reported HBI total scores, is defined as a drop of at least 3 points from baseline HBI total score.

HBI remission, determined based on physician reported HBI total scores, is defined as an absolute score of 4 points or less.

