3.6 Treatment assignment and treatment groups

Given that patients will be followed for 8 years, it is anticipated that patients will switch CD medications while enrolled in the registry. Therefore, a patient's treatment at registry enrollment will most likely not reflect their exposure throughout the study. Three comparisons may be used to reflect these treatment changes over time and provide context for events reported to the registry. See Section 8.1.4 for details.

Treatment start is the recording period (ie, the informed consent date). Only study emergent adverse events will be reported. Study emergent begins at the informed consent through the end of the study.

Treatment by enrollment cohort will consist of two groups:

- Cimzia
- Comparator
 - where comparator includes:
 - Corticosteroids
 - Immunosuppressants
 - Other biologics (e.g. anti-TNFs) other than Cimzia

Enrollment cohort is recorded and will be assumed regardless of the presence of prior or imputed CD medication referring to the other treatment group. These are the default treatment groups.

Some summaries will be repeated by actual treatment at Baseline to examine differences between treatment by enrollment cohort. Actual treatment at Baseline will be summarized in three groups:

- Cimzia at BL
- No Cimzia at BL
- Gap (absence of Cimzia and comparator)

Actual treatment will be used for adverse event tables unless specified otherwise. If a patient received Cimzia up to 70 days prior to baseline (half-life of CZP), the patient is a member of the treatment group "Cimzia at BL". For the calculation of the Hazard Ratio, the group 'Cimzia at BL' is compared against the combined group "No Cimzia at BL" and "Gap".

For malignancies, person-time and events will be categorized into 2 groups:

- Cimzia
- Comparator

where a patient is systematically attributed to Cimzia from their first dose of Cimzia until the end of the study, even after ending or switching from Cimzia.

For acute events, person-time and events will be categorized into 5 groups:

- Cimzia
- Comparator
- Overlap (Cimzia and comparator)
- Gap (absence of Cimzia and comparator)
- Any Cimzia (Cimzia and Overlap)

Example treatment allocations for malignancies and acute events are in Section 11.1, appendix 1.

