4.2 Handling of dropouts or missing data

For HBI scores, all missing values will remain as missing. No attempt will be made to impute missing values. Only observed values will be used in data analyses and presentations.

For both the physician and patient reported HBI, the use of eCRFs will allow the total score to be computed and therefore not require the recording of the total HBI score. However, for the physician reported HBI, if any of the first 4 parameters are missing, then the total HBI score will be set to missing. For the patient reported HBI, if any of the first 3 parameters are missing, then the total HBI score will be set to missing.

Missing safety data, in general, will not be imputed. However, if relationship to CD treatment is missing for an AE, the event will be categorized as having a reasonable possibility of being caused by the treatment for the summary of AEs by relationship.

Concomitant medications will be imputed as described below in accordance with the GSS global conventions document version 1.1.

The following rules are applied to impute partial start and stop dates for medications.

Imputation of Partial Start Dates

- If only the month and year are specified and the month and year of informed consent is not the same as the month and year of the start date, then use the 1st of the month.
- If only the month and year are specified and the month and year of informed consent is the same as the month and year of the start date, then use the date of informed consent.
- If only the year is specified, and the year of informed consent is not the same as the year of the start date, then use January 1 of the year of the start date.
- If only the year is specified, and the year of informed consent is the same as the year of the start date, then use the date of informed consent.
- If the start date is completely unknown, and the stop date is unknown or not prior to the date of informed consent, then use the date of informed consent.

Imputation of Partial Stop Dates

- If only the month and year are specified, then use the last day of the month.
- If only the year is specified, then use December 31 of that year.
- If the stop date is completely unknown, do not impute the stop date.

In the event of ambiguity or incomplete data which makes it impossible to determine whether a medication was concomitant or not, the medication will be considered as concomitant.

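### HBI response and remission by actual treatment at Baseline drop patients once they switch, so later visits describe a selected group, and the term switched is not defined

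*SAP*

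**What the plan says.** SAP 8.2 plans HBI score, change from baseline, response and remission over up to 8 years. For one of its two groupings it adds: "Analyses using actual treatment at Baseline will remove the subject from the summaries after they have switched treatment".

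The denominators are observed cases. For remission, "The number of patients at each visit will be used as the denominator for percentage of HBI remission". For response, "The number of patients with baseline at each post baseline visit will be used as the denominator for percentage of HBI response". SAP 3.2.2 makes both outcomes depend on the score alone: response "is defined as a drop of at least 3 points from baseline HBI total score" and remission "is defined as an absolute score of 4 points or less". Neither definition refers to a change of treatment. On missing HBI, SAP 4.2 says: "No attempt will be made to impute missing values".

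SAP 3.6 sets up the two groupings. Enrollment cohort is Cimzia or Comparator, and of these it says: "These are the default treatment groups". For the other it says: "Actual treatment at Baseline will be summarized in three groups", namely Cimzia at BL, No Cimzia at BL, and Gap. The removal rule is written only for the second grouping. SAP 8.2 names both groupings for HBI score and change from baseline, but names none in the sentence on response and remission.

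**The concern.** A patient who switches leaves both the numerator and the denominator. If switching were unrelated to disease activity, this would cost only precision. Protocol 6.4.1.3 says otherwise: it lists disease severity and past response among the reasons why patients start, stop or stay on a drug. HBI measures that same activity, so the actual-treatment tables condition on a variable linked to their own outcome. SAP 3.6 expects switching during follow-up, and the effect builds up with each visit.

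The data needed to avoid this are being collected. Protocol 4.7 continues follow-up after a drug is stopped, the secondary endpoint in Protocol 6.1.2 has no cut-off at a switch, and the schedule in Protocol 4.5 records the reason for each medication change. The removal rule makes no use of that reason.

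At stake is how the later visits are read. A rising percentage could be taken as growing benefit when part of it reflects who is left, and a gap between groups could reflect unequal removal.

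**Working it through.** The documents state no HBI response, remission or switch rate, so there is no planned figure to reproduce. Every percentage below is an assumption chosen to show direction and range.

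**Step 1: one group.** Let r be remission among patients still on baseline treatment (assumed 50%), s the share switched by a visit (10% to 60%), and q remission at that visit among switchers if they were kept (20% to 60%).

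- Switchers removed (the plan): r
- Switchers kept at their observed score: r(1−s) + qs
- Switchers counted as failures: r(1−s)

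Removal therefore shifts the rate by s(r−q) against keeping switchers, and by rs against counting them as failures.

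At s = 30% the plan shows 50%. Keeping switchers gives:

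- q = 20%: 0.35 + 0.06 = 41%
- q = 35%: 0.35 + 0.105 = 45.5%
- q = 50%: 0.35 + 0.15 = 50%
- q = 60%: 0.35 + 0.18 = 53%

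Counting switchers as failures gives 35%. Over s = 10% to 60%, the shift against keeping switchers is +3 to +18 points at q = 20%, zero at q = 50%, and −1 to −6 points at q = 60%. Against failure scoring it is always upward, by 5 to 30 points.

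**Step 2: what counts as a switch.** SAP 8.2 does not say. Other sections use three meanings, none of them written for HBI:

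- SAP 5.1, censoring rule A: crossing between Cimzia and Comparator.
- SAP 5.1, censoring rule B: one biologic to another biologic.
- Protocol 6.4.1.2, Kaplan-Meier analysis of acute events: any first switch, including one non-Cimzia drug to another.

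Whether moving into Gap, or adding a drug so that Cimzia and comparator overlap, is a switch is not stated.

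**Step 3: two groups with equal true performance.** Take r = 50% and q = 25%. For rules A and B, let 40% of each group switch for failure, so that both groups would show 0.6 × 50% + 0.4 × 25% = 40% if everyone were kept. All Cimzia switchers are removed, so Cimzia shows 50%.

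*Rule A.* If a share x of comparator failure switches go to Cimzia, the comparator shows [0.6 × 0.5 + 0.4(1−x) × 0.25] / (1 − 0.4x).

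| x | Comparator shows | Spurious Cimzia advantage |
|---|---|---|
| 10% | 0.39/0.96 = 40.6% | 9.4 points |
| 30% | 0.37/0.88 = 42.0% | 8.0 points |
| 50% | 0.35/0.80 = 43.75% | 6.25 points |
| 100% | 0.30/0.60 = 50% | 0 |

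*Rule B.* Let a share b of the comparator be on a biologic, and let every biologic failure move to another biologic. The comparator shows [0.30 + 0.4(1−b) × 0.25] / (1 − 0.4b). For b = 20%, 50% and 80% this is 41.3%, 43.75% and 47.1%, an advantage of 8.7, 6.25 and 2.9 points.

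*Any switch.* Both groups now lose all their switchers, and each is raised by s × (50% − 25%). With 30% of Cimzia patients switched, the Cimzia rise is 7.5 points. With 20%, 30%, 40% or 60% of the comparator switched, the comparator rise is 5, 7.5, 10 or 15 points. The net effect on Cimzia minus comparator is +2.5, 0, −2.5 or −7.5 points.

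**Step 4: Gap.** Suppose moving to Gap counts as a switch, and that 20% of a group stop while doing well, with 70% of them in remission. Keeping them gives 0.8 × 50% + 0.2 × 70% = 54%, against 50% when they are removed. Removal then lowers the rate by 4 points.

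**The case against.** The strongest defence is that this is a legitimate pair of displays. The enrollment-cohort grouping is the default and keeps switchers, and the actual-treatment version answers a different question about patients still on their baseline drug. SAP 8.2.1 also plans summaries of switch patterns. HBI is a secondary endpoint in a safety registry, SAP 2.1.1 makes all analyses descriptive, and 8.2 plans no between-group HBI test. Switching is not the same as failure, and counting every safety, access or planned switch as non-response has its own bias. It also cannot be applied to mean scores.

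Most of this stands. It argues for adding a version and not for replacing the on-treatment one. It does not cure the on-treatment tables, and for response and remission the enrollment-cohort version must be inferred from the default, because 8.2 names no grouping there.

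Two stronger readings are tempting. A reader might infer that percentages rise mechanically. That holds only against scoring switchers as failures; against following them up, the rise needs switchers to do worse than stayers. A reader might also infer that removal is heavier for Cimzia, because a comparator patient who changes comparator is still in No Cimzia at BL. That is one reading of an undefined term. Under the any-switch meaning the difference can vanish or reverse. Gap could also push removal toward the comparator: the exposure windows in SAP 3.2.1.3 are 7 days for corticosteroids and 70 for biologics, so if those event-rate windows also governed HBI, steroid patients would reach Gap sooner.

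**Conclusion.** The point holds in a limited form. Followed exactly, SAP 8.2 yields on-treatment response and remission percentages among patients selected partly on disease activity. They overstate benefit if switchers do worse than stayers; Protocol 6.4.1.3 makes that plausible but does not show it. In the illustration with 50% remission among stayers and 30% switched, the shift against keeping switchers runs from +9 points (q = 20%) to −3 points (q = 60%).

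The groups may be affected unequally, in a direction set by the missing definition of a switch. The documents do not establish a bias in favour of Cimzia. Nor do they support a large one: a picture of Cimzia response climbing to 74–91% by year 4 beside a comparator fixed at 40% needs 30–50% of non-responders to leave every year, responders never to switch, response status never to change, and no comparator failure ever to move to Cimzia or improve on its next drug. None of those inputs is in the documents, and Comparator followed by Cimzia is a recurring scenario in SAP Appendix 1.

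The impact is modest, because HBI is secondary and descriptive. The change is still worth making, because such percentages are read as trends and comparisons, and the data to do better are collected.

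**What to change.** Four changes to SAP 8.2:

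1. Define a switch once for the HBI analyses and apply it to all groups, stating how changes within the comparator, Overlap and Gap are counted.
2. Beside the on-treatment response and remission tables, add a version that keeps switched patients in the denominator as non-responders and non-remitters from the switch date, with a split by the recorded reason for the change.
3. Show the number removed at each visit, by group.
4. State that response and remission are also shown by enrollment cohort, and make that the main display.

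The cost is SAP wording and a little more programming. No new data are needed. The drawback is that, in the added version, patients who switch for reasons other than efficacy count as non-responders; the split by reason lets the reader judge how much that matters. The added version does not extend to mean HBI or severity scores, so for those the counts removed are the safeguard.

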8.2.1 Extent of exposure

Length of exposure (weeks), length of exposure category (weeks) and total years of exposure will be presented. This summary will be repeated for each of the exposure definitions presented in Section 3.2.1.

In order to summarize treatments received by both cohorts (ie, treatment switch patterns), descriptive statistics by cohort will be presented for the number of events, the number of exposure patients, and for person-time calculations.

A stratified analysis by cumulative Cimzia exposure may also be performed for malignancy events to identify potential patterns in long-term use of Cimzia.

8.2.2 Adverse Events

Any event reported by the investigator or found in the drug safety database excerpt is considered an adverse event. Investigator and drug safety AEs have been reconciled by the study physician to avoid over reporting.

When an AE is considered serious in either source, it is treated as serious in the analysis and the related coding data is used.

Events reported in the patient survey are not considered confirmed AEs and are excluded from the analysis.

AE tabulations will be done using malignancy rules (for malignancies) separately using acute event rules (all AEs) unless otherwise specified.

A summary of study-emergent AEs, including the number of events reported, the number and percentage of patients reporting at least one AE, the number and percentage of patients reporting at least one AE of Interest, the number and percentage of patients with at least one serious AE (SAE), and the number and percentage of deaths will be presented. In addition, the number and percentage of patients reporting at least one study-emergent treatment-related AE, the number and percentage of patients reporting at least one study-emergent treatment-related AE of Interest, and the number and percentage of patients with at least one study-emergent treatment-related SAE will also be reported. AE summaries will be produced on the enrolled cohort as well as the malignancy/acute event rules.

Study-emergent AEs are those which first occur or increase in relationship to treatment after the first dose of any CD drug following enrollment.

A breakdown of the number and percentage of patients reporting each AE as well as the number of AEs, categorized by SOC, HLT, and PT coded according to MedDRA, will be presented. Note that patients are only counted once within each SOC, HLT, or PT. Uncoded AEs will be summarized in unknown SOC, HLT and PT. This will be produced for the enrolled cohort as well as both the malignancy and acute event rules.

A further tabulation of these data, broken down by relationship to treatment, will be presented. Patients with multiple events within a particular body system or preferred term will be counted under the category of their most drug-related event within that SOC, HLT or PT. Relationship to treatment is categorized as related or not related as collected on the eCRF.

A breakdown of the number and percentage of patients reporting each AE as well as the number of AEs, categorized by SOC, HLT, and PT coded according to MedDRA, will be presented, including only patients in the Enrolled Set with multiple occurrences of any AE.

All AEs will be coded using the most recently available version of MedDRA available at each analysis (and version 20.0 for interim analysis 2) and all AEs collected on the eCRF will be included in a listing (except patient survey data). SOC, HLT and PT terms will be presented by decreasing frequency.

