5.6 UCB Pharmacovigilance Reporting

Adverse events collected from the registry that occur within 70 days of last Cimzia dose will be included in UCB's safety database and reported to the FDA as per regulatory reporting guidelines. Registry cases of malignancy, death, and pregnancy will be included in UCB's safety database and reviewed and evaluated for FDA reporting even if the event occurs after 70 days of last Cimzia dose. Any reports received prior to start of the registry and after completion of the study will be evaluated and reported as per standard UCB pharmacovigilance plans for spontaneous reporting.

Figure 5–1: Event reporting process

AE=adverse event; EDC=electronic data capture; SAE=serious adverse event

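### The SAP adds events and seriousness upgrades from a drug safety database whose only stated entry rule is tied to Cimzia dosing, so ascertainment is differential unless the excerpt covers comparator cases equally

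*SAP*

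**What the plan says.** SAP 8.2.2 sets four source rules.

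- Inclusion: "Any event reported by the investigator or found in the drug safety database excerpt is considered an adverse event".
- Seriousness and coding: "When an AE is considered serious in either source, it is treated as serious in the analysis and the related coding data is used".
- Reconciliation: "Investigator and drug safety AEs have been reconciled by the study physician to avoid over reporting".
- Patient surveys: "Events reported in the patient survey are not considered confirmed AEs and are excluded from the analysis".

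The SAP does not say which database the excerpt comes from, how it was selected, or which patients it covers.

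The only safety database that the documents describe is the sponsor's, in Protocol 5.6. For events in general: "Adverse events collected from the registry that occur within 70 days of last Cimzia dose will be included in UCB's safety database". A further sentence reads: "Registry cases of malignancy, death, and pregnancy will be included in UCB's safety database". It goes on to lift the 70-day limit for those cases, and it still refers to the last Cimzia dose.

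Protocol 5.4 sends all SAEs and AEs of interest, whatever the treatment, from the EDC system to the CRO for assessment and processing under the sponsor's procedures.

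**The concern.** The registry exists to compare safety on Cimzia with safety on other Crohn's disease treatment (Protocol 3, SAP 2.1.1). That comparison needs events to be found and classified in the same way in every treatment group. If the excerpt follows Protocol 5.6, an event on Cimzia can be added, made serious or recoded from a second source, while an event on a comparator rests on the site's entry alone.

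These counts feed the hazard ratios in SAP 8.1.3, the incidence rates and Poisson comparison in 8.1.4, and the adjusted rate ratios in 8.1.5. Propensity matching and covariate adjustment do not correct for differential ascertainment. A raised ratio could then not be told apart from the effect of the extra source.

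**Working it through.** The plan states no figure for this point, so there is none to reproduce. The check sets the rules side by side, asks which endpoints they can reach, and then gives an illustration on assumed inputs.

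**1. Coverage by treatment time, on the natural reading of Protocol 5.6**

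| Source | Up to 70 days after a Cimzia dose | Pure comparator or gap time |
|---|---|---|
| Investigator report (eCRF) | counts | counts |
| Safety database, general AEs | entry stated | no entry route stated |
| Safety database, malignancy, death, pregnancy | entry stated | ambiguous |
| Patient survey | excluded | excluded |

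SAP 3.2.1.3 gives biologics, Cimzia included, a 70-day exposure window. Appendix 1 of the SAP adds that window to each treatment period before Overlap is defined. The database window therefore coincides with the time that the SAP labels Cimzia or Overlap, so any asymmetry lies along the contrasts in 8.1.3. The exception for malignancy, death and pregnancy suggests that the 70-day rule otherwise limits entry; without a limit it would not be needed.

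**2. Endpoints that can be affected**

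SAP 8.2.3 draws serious infections, MACE, cytopenias, serious bleeding and serious skin reactions from serious events. An upgrade creates an endpoint event only where a nonserious record exists. Protocol 5 asks sites to enter nonserious events only if they are AEs of interest. Protocol 5.2 lists infections, bleeding and skin reactions already restricted to serious ones, so few nonserious records should exist for those. Cytopenias and congestive heart failure are listed without that restriction. A nonserious cytopenia can be upgraded into the SAP's cytopenia endpoint, and nonserious heart failure into MACE, which includes serious heart failure terms.

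Malignancies are selected by SMQ and not from the serious subset. An upgrade alone creates no malignancy; only a database-only case or a recoding could.

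Added events and upgrades can only raise the count. Recoding could move an event into or out of a category.

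**3. Size, on assumed inputs**

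Let the database add a fraction f to the Cimzia count and nothing to comparator. Reported ratio = true ratio × (1 + f). At a true ratio of 1.0, f = 5%, 10% and 20% give 1.05, 1.10 and 1.20. As a scale, Protocol 6.3 plans to detect 1.5 for serious infections, and 0.20 / 0.50 = 40% of that excess.

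To see what could produce such an f, let s be the share of true events that the investigator captures and r the share of missed events that the database recovers, on Cimzia only. Then f = (1 − s) × r / s. The last column is the chance of a nominal two-sided p < 0.05 with D = 191 events, the number needed for 80% power at a ratio of 1.5 with equal person-time: 4 × (1.960 + 0.842)² / (ln 1.5)² = 191. The chance is Φ(m − 1.96) + Φ(−m − 1.96), with m = √(D/4) × ln(1 + f).

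| s | r | f | Reported ratio | Chance of p < 0.05 |
|---|---|---|---|---|
| 95% | 50% | 0.026 | 1.03 | 5.4% |
| 90% | 50% | 0.056 | 1.06 | 6.6% |
| 90% | 100% | 0.111 | 1.11 | 11.3% |
| 80% | 50% | 0.125 | 1.13 | 12.9% |
| 80% | 100% | 0.250 | 1.25 | 33.8% |
| 70% | 100% | 0.429 | 1.43 | 69.3% |

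The distortion is small if site capture is near complete. It nears 1.5 only if about 30% of events are missed and all of them are recovered.

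**The case against.** A reader might infer that the database holds only Cimzia cases, that a patient never given Cimzia cannot enter it, and that every ratio in the study, malignancy included, is therefore biased. The documents do not support that much.

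- Protocol 5.6 says what goes in and does not expressly exclude the rest. Protocol 5.4 forwards events from all patients. Superseded text in Protocol 14.1 had registry events sent to the sponsor's safety group without restriction by arm, so some early comparator cases may be present.
- The SAP never equates its excerpt with the database of Protocol 5.6. The Analysis Data Reviewers Guide cited in SAP 3.1 may describe the source handling.
- The sentence on malignancy, death and pregnancy can be read as covering all registry cases. That would give equal coverage for the primary outcome.
- Cases under 5.6 are collected from the registry, so the database is not an independent second search. Its main yield may be upgrades and recoding.
- The analyses are declared descriptive, and extra events counted on Cimzia would not hide a Cimzia risk.

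The first four points stand, and they make the concern conditional. They do not answer it: 5.4 concerns processing while 5.6 is the specific rule on entry, and the SAP neither states equal coverage nor checks it. Reconciliation is aimed at over-reporting, not at equal capture. The last point helps little, because a ratio raised by ascertainment misdescribes the comparison whether or not it is tested.

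**Conclusion.** The concern holds in conditional form. SAP 8.2.2 lets a second source add events, upgrade seriousness and supply coding, and the only entry rule given for such a source depends on Cimzia dosing. Unless the excerpt covers comparator cases equally, ascertainment and seriousness classification differ by treatment, and added events and upgrades push Cimzia/comparator ratios upward. The clearest exposure is in cytopenias and in heart failure within MACE. For malignancy it is uncertain.

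The conclusion assumes that the excerpt comes from the database in Protocol 5.6 and that its 70-day rule limits entry. Both are natural readings, but neither is stated. The range of 1.05 to 1.20 rests wholly on an assumed f of 5% to 20%; the documents give no yield for the database.

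**What to change.** In SAP 8.2.2:

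1. State which database the excerpt comes from and its coverage by treatment, with malignancy, death and pregnancy addressed separately.
2. Carry a source flag in the analysis dataset for the event, its seriousness and its coding.
3. Tabulate by treatment group the events found only in the database and those made serious or recoded only by it.
4. Run the comparative analyses in 8.1.3 to 8.1.5 on eCRF-reported events, with eCRF seriousness and coding, in all groups. Present them alongside the either-source analysis.
5. State in advance that, if coverage proves unequal, the eCRF-only comparison is the basis for between-treatment ratios, with all database events still reported in full.

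The cost is SAP wording, a flag on data that are already reconciled, and a second set of comparative tables. The downside is that some confirmed Cimzia events would not count in the eCRF-only ratio. For that reason both analyses should be shown, and neither should be dropped before coverage is known.
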